# 7.3.8 Electronic Patient Diary

Subject compliance with daily administration of cinacalcet will be collected using a handheld eDiary. The eDiary will collect date, time and amount of cinacalcet taken each day. Subjects will use the eDiary daily beginning on day 1 and completing at their week 28 study visit. It is expected that children under the age of 12 will have their parent(s) or legal guardian(s) complete the eDiary daily. Children  $\geq$  12 years of age may either have their parent(s) or legal guardian(s) complete the eDiary daily or do this themselves under the supervision of their parent(s) or legal guardian(s). The subjects will be instructed to bring their eDiary with them to every study visit. The data entered into the eDiary will be available to the investigator and/or study coordinator on a daily basis to enable ongoing reviews of subject compliance. The data collected will be reviewed with the subject by the investigator and/or study coordinator during the weekly study visits. The investigator and/or study coordinator will also reconcile any discrepancies between the eDiary and the IP accountability data during the weekly study visits. Reasons for discrepancies will be documented and subjects and/or parents/legal guardians counseled on the importance of compliance with the administration of cinacalcet during the trial. The data collected will be captured in the study database.

Refer to Section 6.2.3.2 for additional information regarding the measures of compliance for this study and the eDiary manual for additional details.

# 7.3.9 Ionized Calcium

All ionized calcium values will be collected as specified in the Schedule of Assessments for identification of potential hypocalcemia. Ionized calcium values will be obtained either per routine practice at the clinical site or using a point of care device provided by

CONFIDENTIAL

Page 51 of 79

**AMCEN**'

Amgen. The clinical site will document the method that is being used to obtain the ionized calcium for each subject enrolled at the site and ensure that this remains consistent for the duration of the trial. All measurements should occur on the day of the study visit prior to the administration of cinacalcet. For sites that use the point of care device provided by Amgen, refer to the device manual provided for further information.

The measurements obtained will be entered into the IVR/IWR system at each study visit and entered into the eCRF.

In addition, cCa values from the central laboratory will be collected as specified in the Schedule of Assessments. These cCa values will be utilized for monthly dose titration visits.

## 7.3.10 Adverse Events

Adverse events will be collected in the eCRF for each subject at all study visits. Targeted questions regarding hypocalcemia, seizures and infections will be asked and data will be entered into the eCRF at each study visit.

All clinically significant (according to the investigator's judgment), laboratory abnormalities will be reported as adverse events. In assessing clinical significance of a low serum calcium value, the investigator should consider factors such as presence of clinical symptoms associated with hypocalcaemia, dose adjustment of cinacalcet or concomitant medications (eg, vitamin D, phosphate binders). In addition, the investigator should indicate on the eCRF whether hypocalcemia was symptomatic, and if so provide the accompanying symptoms.

Serious adverse events that occur in a subject from the date of the first dose through 30 days after the last dose of IP will be recorded in the adverse event eCRF. All adverse events that occur from the date of the first dose through 30 days after the last dose of IP will be recorded in the adverse event eCRF. Refer to Section 9 for additional information.

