# 2.5 Studies Eligible to Roll-over to 201401592.5.1 Amgen Study 20130356

Amgen Study 20130356 is a phase 3 randomized, multicenter, open-label, controlled study. In Study 20130356, cinacalcet is being evaluated in pediatric subjects enrolled between the ages of 6 and < 18 years, with SHPT and CKD receiving either

CONFIDENTIAL

Page 16 of 79

**AMCEN**"

hemodialysis or peritoneal dialysis. Approximately 48 subjects are planned to be randomized into the study to one of two treatment arms in a 1:1 allocation ratio; daily oral administration of cinacalcet in addition to SOC or SOC only. Once randomized, the expected treatment period in 20130356 is 20 weeks with a 4-week safety follow-up period. Subjects who are eligible for and enroll in the 20140159 extension study will do so at the completion of the 20-week treatment period in 20130356 or following Study 20130356 termination and within 7 days of day 1 of 20140159, unless there is an administrative delay. The end of study (EOS) procedures for an individual subject will occur at the same time as the end of investigational product (EOIP) visit for subjects enrolling in Study 20140159. The 4-week safety follow-up period in 20130356 will not apply for these subjects.

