# 4. SUBJECT ELIGIBILITY

Before any study-specific activities/procedure, written informed consent must be obtained (see Section 11.1). In addition to written informed consent from a legally acceptable representative, the assent of the child also must be obtained, as appropriate and if requested by the institutional review board/independent ethics committee (IRB/IEC).

Subjects from the cinacalcet arm of Study 20130356 or subjects in Study 20110100 who had their dose withheld at the EOIP visit, may enroll in this study if they meet eligibility criteria but will not restart dosing until the criteria for restarting dosing, defined in Section 6.2.3, are met.

Subjects who were  $\leq$  18 years old at week 20 in the 20130356 study or at the time of study termination, are eligible to enter this Study 20140159 even if they have already turned 18 years of age or are due to turn 18 years of age during their planned participation in the 20140159 study.

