#### 9.2.2 Reporting Procedures for Serious Adverse Events

The investigator is responsible for ensuring that all serious adverse events observed by the investigator or reported by the subject that occur from the date of the first dose through 30 days after the last day of the dosing interval of IP or end of study visit (whichever is later) are recorded in the subject's medical record and are submitted to Amgen. All serious adverse events must be submitted to Amgen within 24 hours following the investigator's knowledge of the event via the serious adverse event form.

After the protocol-required reporting period defined above, the investigator does not need to actively monitor subjects for serious adverse events. However, if the

AMGEN

Page 58 of 79

investigator becomes aware of a serious adverse event after this protocol-required reporting period, the investigator will report the event to Amgen within 24 hours following the investigator's knowledge of the event. Serious adverse events reported outside of the protocol-required reporting period will be captured within the safety database as clinical trial cases for the purposes of expedited reporting.

See Appendix A for a sample of the Serious Adverse Event Worksheet.

The investigator must assess whether the serious adverse event is possibly related to any study-mandated activity or procedure. This relationship is indicated by a "yes" or "no" response to the question: "Is there a reasonable possibility that the event may have been caused by a study activity/procedure"?

The investigator is expected to follow reported serious adverse events until stabilization or reversibility.

New information relating to a previously reported serious adverse event must be submitted to Amgen. All new information for serious adverse events must be sent to Amgen within 24 hours following knowledge of the new information. The investigator may be asked to provide additional follow-up information, which may include a discharge summary or extracts from the medical record. Information provided about the serious adverse event must be consistent with that recorded on the applicable eCRF (eg, Adverse Event Summary eCRF).

If a subject is permanently withdrawn from protocol-required therapies because of a serious adverse event, this information must be submitted to Amgen.

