**Study Day 1**

The date that the initial dose of IP is administered in Study 20140159. For subjects who didn't take any IP throughout the study, leave as missing.

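### AE and SAE recording opens only at the first dose, although children on a cinacalcet hold may enrol undosed; this conflicts with the all-visits collection rule and leaves pre-restart events without a clear duty to record or report

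*Protocol*

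**What the plan says.** **Recording window.** Protocol 7.3.10 records "Serious adverse events that occur in a subject from the date of the first dose through 30 days after the last dose of IP" and, for non-serious events, "All adverse events that occur from the date of the first dose through 30 days after the last dose of IP". The synopsis and 9.2.1 use the same start. Section 9.2.2 applies it to the reporting duty, covering SAEs "that occur from the date of the first dose through 30 days after the last day of the dosing interval of IP" or to the end-of-study visit if later.

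**Enrolment without dosing.** Under Protocol 4, children whose dose was withheld at the parent end-of-treatment visit "may enroll in this study if they meet eligibility criteria but will not restart dosing until the criteria for restarting dosing" are met. Sections 6.2.3.1.1 and 6.2.3.1.2 set dosing-start conditions even for gaps of more than 1 month, so an undosed interval at roll-over is planned for.

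**Parent follow-up.** For 20130356 roll-overs, Protocol 2.5.1 states: "The 4-week safety follow-up period in 20130356 will not apply for these subjects". Under 2.5.2, the 2-week follow-up of 20110100 is waived only for those entering at study termination. Completers keep it and are screened during it (3.1.2).

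**Text pointing the other way.** Section 7.3.10 opens with "Adverse events will be collected in the eCRF for each subject at all study visits" and adds "Targeted questions regarding hypocalcemia, seizures and infections will be asked and data will be entered into the eCRF at each study visit". Section 7.2.2 lists AE and SAE reporting on day 1, and Table 4 shows both as recorded continuously.

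**Analysis.** SAP 6.2 defines Study Day 1 as the first extension dose: "For subjects who didn't take any IP throughout the study, leave as missing". Treatment-emergent events for 20140159 alone count from that day (SAP 6.4), and the Safety Analysis Set needs at least one dose (SAP 7.2).

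**The concern.** For most children the day 1 visit and the first extension dose coincide, and the two sets of rules agree. For a child on hold they separate. The day 1 visit takes place, the parent study is closed, weekly visits begin, and the event that opens the recording window has not happened. If the child never restarts, it never happens.

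These children may have been taken off drug for low calcium, low iPTH or an adverse event. The primary endpoint is the incidence of events of interest, including hypocalcemia and convulsions. A site that follows 9.2.1 and 9.2.2 as written has no duty to report an SAE arising before restart. The catch-all in 9.2.2 does not help, because it covers only SAEs learned of after the reporting period, not before its start. At stake are SAE oversight during the hold and, in the combined analysis, follow-up time that is counted while its events may be missing.

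**Working it through.** The plan states no figure on this point, so the check is a comparison of rules, followed by arithmetic to size the consequence.

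**Rules for a child enrolled on hold, between the day 1 visit and restart**
- Section 7.3.10, opening sentences: collect AEs and ask the targeted questions at each visit. Not tied to dosing.
- Section 7.2.2 and Table 4: AE and SAE recording from the day 1 visit. Not tied to dosing.
- Synopsis, 7.3.10 (recording sentences) and 9.2.1: record from first dose. Window not yet open.
- Section 9.2.2: report SAEs from first dose. Window not yet open.
- SAP 9.3.2.1: the eCRF asks whether an event began before the first dose of investigational product, so the form can hold such events.
- SAP 6.4, 20140159 only: an event before Study Day 1 is not treatment-emergent.
- SAP 6.4, combined studies: treatment-emergent from the first-ever cinacalcet dose, so a recorded hold-period event counts for a child who restarts.
- SAP 6.1, follow-up time for the adjusted rate: end of study minus first-ever cinacalcet dose, plus 1 day. Hold time is in the denominator.
- SAP 7.2: a child never dosed in the extension is outside the Safety Analysis Set, so is in neither numerator nor denominator.

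The first two rules contradict the next two. Where the narrower one is followed, the combined rate counts time without its events.

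**Who could be on hold.** 48 subjects randomised 1:1 gives 48 / 2 = 24 in the cinacalcet arm of 20130356. With 30 from 20110100 (SAP 3.2), at most 24 + 30 = 54 of 78 roll-overs had prior cinacalcet. How many arrive on hold is not stated.

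**Time outside the first-dose window.** Hold lengths of 2, 4 and 8 weeks are assumptions.
- Share of the 32-week extension: 2/32 = 6.2%, 4/32 = 12.5%, 8/32 = 25.0%.
- Share of combined follow-up for a 20130356 cinacalcet-arm completer (20 + 32 = 52 weeks): 2/52 = 3.8%, 4/52 = 7.7%, 8/52 = 15.4%.
- Share for a 20110100 completer (26 + 32 = 58 weeks): 2/58 = 3.4%, 4/58 = 6.9%, 8/58 = 13.8%.
- A child who never restarts but stays to week 32: 32 × 7 = 224 days.

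**The case against.** The best reply is that collection is in fact stated. A reader might infer from the first-dose wording that children on hold have no AE collection at all. The documents do not support that: 7.3.10, 7.2.2, Table 4 and the eCRF item all point to collection before dosing. Section 12.4 also makes investigators responsible for data collection in subjects not receiving protocol-required therapies. This stands, and it makes the defect a contradiction rather than an absence. It does not remove the defect, because the SAE reporting duty in 9.2.2 carries only the narrower start.

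A reader might also infer that hold-period events fall in neither study's collection period. That cannot be shown. The parent protocols' AE windows are not in these documents and may cover part of a hold. For 20110100 completers the parent follow-up is not lost.

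A third tempting inference is a quantified downward bias in the primary endpoint, such as 1/78 = 1.3 percentage points per missed child. That does not follow. A never-dosed child leaves both numerator and denominator. A child who restarts changes subject incidence only if no event of the same category is recorded later. Counting from the first dose in the study is a legitimate definition for the 20140159-only table, and the combined analysis complements it.

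Eligibility also filters risk. Exclusion 217 removes ongoing related events that are grade 3 or higher or clinically significant, and exclusion 211 removes new or worsening seizures. Ionized calcium is checked weekly during a hold. These points lower the expected number of events, but holds triggered by calcium or iPTH thresholds can still enter.

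**Conclusion.** The point holds as an internal conflict with a practical consequence. Four places start AE or SAE recording or reporting at the first dose, while other text in the same protocol expects collection at every visit from day 1. Taken literally, the first-dose rule leaves events between enrolment and restart, or throughout the study for a child never re-dosed, with no duty to record or report them. For children who restart, the combined adjusted rate would then be diluted by the uncollected share of follow-up: 3.4% to 15.4% for the affected child under assumed holds of 2 to 8 weeks. The effect on the overall rate cannot be computed, because neither the number of children on hold nor the length of holds is given.

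This rests on reading the first dose in 7.3.10 as the first extension dose. The Study Day 1 definition supports that reading, but 7.3.10 does not say so. The matter is worth correcting because it concerns SAE reporting in children and the remedy is cheap.

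**What to change.** **Protocol.** In the synopsis, 7.3.10, 9.2.1 and 9.2.2, start AE and SAE collection and reporting at enrolment (the day 1 visit), whether or not a dose is given. This brings those sections into line with the all-visits sentence, 7.2.2 and Table 4.

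**SAP.** Keep the 20140159-only treatment-emergent definition. Add a separate listing of events between enrolment and the first extension dose, and of events in enrolled subjects who were never dosed. SAP 9.3.2.1 already shows incomplete dates as they stand in listings, so no new date anchor is needed. In the combined analysis, count hold-period events as SAP 6.4 already provides, so that the numerator matches the follow-up time.

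**Cost.** Wording changes in four protocol places, one added listing, a few more AE records and possibly a slightly higher reported combined rate. Visits are already weekly and the eCRF already has the pre-dose item. No hold or restart rule changes.

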#### 7.3.11 Laboratory Assessments

All study laboratory samples, with the exception of the ionized calcium samples, will be processed and sent to the central laboratory for assessment. The central laboratory will provide a study manual that outlines handling, labeling, and shipping procedures for all blood samples. All blood samples will be obtained via venipuncture prior to the administration of IP. The date and time of the sample collection will be recorded in the source documents at the site.

#### CONFIDENTIAL

Page 52 of 79

**AMGEN**°

Table 5 below outlines the specific analytes that will be assessed at the central laboratory:

	Table 5. Analytes					
Serum Chemistry	Hematology					
Bicarbonate	Hemoglobin					
Blood Urea Nitrogen	Hematocrit					
Chloride	Platelets					
Creatinine	White blood cell count					
Potassium	Red blood cell count					
Sodium	Liver Function Tests					
Total Protein	ALT					
Total Bilirubin	AST					
Phosphorus	Alk Phos					
Other						

Table 5 Analytes

iPTH, Albumin, Calcium

Serum Pregnancy (females of child bearing potential)

Corrected Calciuma

Total and bioavailable testosterone (male)

BALP, NTx, CTx, P1NP, 25(OH) Vitamin D, FGF23 (not required for subjects from 20110100)

a Corrected calcium will be determined by the central laboratory using the following formula, where 4.0 represents the average albumin level. No correction will be made if the

serum albumin level is  $\geq$  4.0 g/dL.

Corrected calcium (mg/dL) = Measured total serum calcium (mg/dL) + 0.8 (4.0-serum albumin [g/dL])

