- 215 Either new or recurrent cardiac ventricular arrhythmias requiring a change in treatment within 10 days prior to screening visit or day 1 of Study 20140159 screening
- 216 Hepatic impairment indicated by elevated levels of hepatic transaminase or bilirubin (aspartate aminotransferase [AST] ≥ 1.5 × upper limit of normal [ULN] OR alanine aminotransferase [ALT] ≥ 1.5 × ULN OR total bilirubin ≥ 1 × ULN per institutional laboratory range) during screening

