#### 6.3 Hepatotoxicity Stopping and Rechallenge Rules

Subjects with abnormal hepatic laboratory values (ie, alkaline phosphatase [ALP], aspartate aminotransferase [AST], alanine aminotransferase [ALT], total bilirubin [TBL]) and/or international normalized ratio (INR) and/or signs/symptoms of hepatitis (as described below) may meet the criteria for withholding or permanent discontinuation of Amgen IP or other protocol-required therapies as specified in the Guidance for Industry Drug-Induced Liver Injury: Premarketing Clinical Evaluation, July 2009.

Cinacalcet is metabolized by the liver. Subjects with moderate to severe hepatic impairment have the potential for 2- to 4-fold higher area under the curve (AUC) of cinacalcet concentration and may require additional follow-up.

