# ional Withholding of Amgen Investigational

#### 6.3.2 Criteria for Conditional Withholding of Amgen Investigational Product and Other Protocol-required Therapies Due to Potential Hepatotoxicity

For subjects who do not meet the criteria for permanent discontinuation of Amgen IP outlined above and have no underlying liver disease, and eligibility criteria requiring normal transaminases and TBL at baseline or subjects with underlying liver disease and baseline abnormal transaminases, the following rules are recommended for withholding of Amgen IP and other protocol-required therapies:

	5 5
Baseline AST or ALT value	AST or ALT elevation
Any	> 8 × ULN at any time
Any	> 5 × ULN but < 8 × ULN for $\ge$ 2 weeks
Any	> 5 × ULN but < 8 × ULN and unable to adhere to enhanced monitoring schedule
Any	> 3 × ULN with clinical signs or symptoms that are consistent with hepatitis (such as right upper quadrant pain/tendemess, fever, nausea, vomiting, jaundice).

• Elevation of either AST or ALT according to the following schedule:

- OR: TBL > 3 × ULN at any time
- OR: ALP > 8 × ULN at any time

Cinacalcet should be withheld pending investigation into alternative causes of DILI. If investigational product(s) is withheld, the subject is to be followed according to recommendations in Appendix A for possible DILI. Rechallenge may be considered if an alternative cause for impaired liver tests (ALT, AST, ALP) and/or elevated TBL, is discovered and the laboratory abnormalities resolve to normal or baseline (Section 6.3.3).

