# 7. STUDY PROCEDURES

# 7.1 Schedule of Assessments

Screening assessments and study procedures required for each visit are outlined in this section and the Schedule of Assessments (Table 4). The informed consent, and assent if applicable, must be obtained prior to performing any screening or study procedures.

CONFIDENTIAL

AMGEN

Product:	Cinacalcet HCI								
Protocol	Number:	20140159							
Date: 01	June 201	6							

							٦	a b	le 4	I. S	Sch	edı	lle	of /	١ss	ess	me	nts	;												
	Screening							Treatment Period (Week)																FU F	Period						
	Week -1	7	1	2	3	4	5	6	7	8	9	10	11	12	13	14	15	16	17	18	19	20	21	22	23	24	25	26	27	EOIP W28	ET/EOS W32
GENERAL & SAFETY A	SSESSMENT	s																					-	-		-		-			
Informed consent,	×																														
Assent (if applicable)	X																														
Medical/Surgical History		Х																													
12-lead ECG		Х																												X	Х
Physical Exam		X 																													X
Height, Tanner Stage		X 																													X
Dry Weight		X 																													Х
Dialysate Ca																															
Concentration		X																													
Blood Pressure, Heart		X 	1		x				x				x				v				v				v				x	x	×
Rate		X			×				×				×				X				X				X				×	×	X
Concomitant	X 		_												0															V	V
Medications 	~												Re	ecord	Cor	tinuc	usiy													X	X
Patient Diary Review		X1	X	X	X	X	X	X	X	X	X	X	X	X	Х	X	X	X	Х	X	X	X	X	X	X	X	X	X	X	Х	
Adverse events 			_										R	ecor	d Co	ntinu	ously	,												X	Х
Serious Adverse events 													R	ecor	d Co	ntinu	ously	/												Х	Х
LABORATORY ASSESS	MENTS																														
Ionized Ca		X	X	X	X	X	X	X	X	X	X	X	X	X	Х	X	X	X	Х	X	X	X	X	X	X	X	X	X	Х	Х	
Liver Function Tests	X 	Х											X												X						Х
Chemistry, hematology, 25(OH)Vit D 	X 	X 																												х	X
Ca, Albumin, cCa, P	X 	X 	X		X				X				X				X				X				X					X	Х
iPTH	X 	X1		1	X				X		-		X				X				X				X	1	-	1		X	X
Total & Bioavail Testosterone (male)		X 1																												x	
Serum Pregnancy Test (females of child bearing	х																														x
potential) BIOMARKER ASSESSM	ENTS																														
BALP, NTx, CTx, P1NP, FGF 23 		X 1																												х	

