**AMGEN** 

# 7.2.3 Treatment

The following procedures will be completed during the 28-week treatment period at the times designated in the Schedule of Assessments (Table 4). Study visits will occur weekly  $\pm$  3 days. All blood samples for laboratory assessments for hemodialysis subjects are to be collected prior to initiating the dialysis session during the visit. Cinacalcet will be dispensed to subjects to take home for daily administration at the conclusion of the study visit weekly.

The following procedures and assessments will be completed at the times designated in the Schedule of Assessment (Table 4, Section 7.1) and recorded on the eCRF:

- concomitant medications
- documentation of subject compliance with daily administration of cinacalcet
  - o patient diary review
  - o counts of returned bottles of tablets/capsules/suspension
- adverse events, including signs and symptoms of hypocalcemia, seizures, and infections
- serious adverse events
- ionized calcium
- central laboratory assessments including the following:
  - o serum calcium, serum albumin, and calculation of cCa, phosphorous
  - o iPTH
  - LFT (weeks 11 & 23)

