# 7.2.5 Early Termination

Subjects who discontinue participation in the study prior to week 28 will be asked to complete an early termination visit and should have all EOIP and EOS evaluations performed as outlined in the Schedule of Assessments and in Sections 7.2.4 and 7.2.6.

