# Additional Clinical Assessments and Observation

All subjects in whom investigational product(s) or protocol-required therapies is/are withheld (either permanently or conditionally) due to potential DILI as specified in Sections 6.3.1 and 6.3.2 or who experience AST or ALT elevations > 3 x ULN are to undergo a period of "close observation" until abnormalities return to normal or to the subject's baseline levels. Assessments that are to be performed during this period include:

- Repeat AST, ALT, ALP, bilirubin (total and direct), and INR within 24 hours
- In cases of TBL > 2x ULN or INR > 1.5, retesting of liver tests, BIL (total and direct), and INR is to be performed every 24 hours until laboratory abnormalities improve

Page 75 of 79

Testing frequency of the above laboratory tests may decrease if the abnormalities stabilize or the investigational product(s) or protocol-required therapies has/have been discontinued AND the subject is asymptomatic.

- Initiate investigation of alternative causes for elevated AST or ALT and/or elevated TBL:
- Obtain complete blood count (CBC) with differential to assess for eosinophilia
- Obtain serum total immunoglobulin IgG, Anti-nuclear antibody (ANA), Anti Smooth Muscle Antibody, and Liver Kidney Microsomal antibody 1 (LKM1) to assess for autoimmune hepatitis
- Obtain serum acetaminophen (paracetamol) levels
- Obtain a more detailed history of:
  - Prior and/or concurrent diseases or illness
  - o Exposure to environmental and/or industrial chemical agents
  - Symptoms (if applicable) including right upper quadrant pain, hypersensitivity-type reactions, fatigue, nausea, vomiting and fever
  - o Prior and/or concurrent use of alcohol, recreational drugs and special diets
  - Concomitant use of medications (including non-prescription medicines and herbal and dietary supplements), plants, and mushrooms
- Obtain viral serologies
- Obtain CPK, haptoglobin, LDH, and peripheral blood smear
- Perform appropriate liver imaging if clinically indicated
- Obtain appropriate blood sampling for pharmacokinetic analysis if this has not already been collected
- Obtain hepatology consult (liver biopsy may be considered in consultation with an hepatologist)

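### Total bilirubin sits in the chemistry panel, so the stand-alone bilirubin withholding rule has no scheduled test during dosing

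*Protocol*

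**What the plan says.** - **Analyte table (protocol 7.3.11, Table 5).** "Total Bilirubin" appears in the serum chemistry column. The liver function block holds ALT, AST and alkaline phosphatase only.
- **Schedule (protocol 7.1, Table 4).** The row "Chemistry, hematology, 25(OH)Vit D" is marked at day 1, week 28 and week 32. It is also marked at screening, but only when more than 14 days have passed since the last parent-study visit. The liver function row is marked at day 1 and weeks 11, 23 and 32, with the same conditional screening draw.
- **Visit text.** Section 7.2.3 puts liver function tests at weeks 11 and 23 and lists no chemistry panel during treatment. Section 7.2.4 (week 28) has chemistry but no liver function tests. Section 7.2.6 (week 32) has both.
- **Early leavers (7.2.5).** Subjects who stop before week 28 "should have all EOIP and EOS evaluations performed", which brings in a chemistry panel.
- **Withholding rule (6.3.2).** "TBL > 3 × ULN at any time" is joined by OR to the transaminase and alkaline phosphatase criteria, so it acts without them.
- **Reflex testing (Appendix A).** Bilirubin is measured in subjects whose drug is withheld for potential liver injury "or who experience AST or ALT elevations > 3 x ULN".
- **SAP 10.7.2.** Total bilirubin is placed under liver function tests, with a one-way shift table for increases.

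**The concern.** The protocol sets a safety rule on a laboratory value and then schedules no measurement of that value while the rule could act. The other stand-alone criterion in 6.3.2, alkaline phosphatase above 8 × ULN, is tested at weeks 11 and 23. Bilirubin is not.

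The protocol's own text treats bilirubin as informative alone. Exclusion 216 describes "Hepatic impairment indicated by elevated levels of hepatic transaminase or bilirubin" and lets bilirubin at or above 1 × ULN exclude a subject by itself. Section 6.3 warns that moderate to severe hepatic impairment carries the "potential for 2- to 4-fold higher area under the curve (AUC) of cinacalcet concentration", in a study where children are titrated upwards. An isolated rise does not prove impairment, but 6.3.2 asks for the drug to be held and the cause investigated once the threshold is passed. During dosing, that request depends on someone deciding to test.

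There is also a reporting effect. For subjects who stay on study, the SAP's worst-grade shift in bilirubin rests on two scheduled post-baseline values: one at the end of dosing and one after it.

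**Working it through.** No sample size or error rate is involved. The check maps each analyte to its panel (Table 5), each panel to its visits (Table 4 and sections 7.2.2 to 7.2.6), and each visit to its target day.

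**Inputs.** SAP 6.2, windows for vital signs and all other labs: day 1 = 1, week 11 = 78, week 23 = 162, week 28 = 197, week 32 = 225. Maximum enrolment is 78 (protocol 3.3). The subject considered does not terminate early.

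**Scheduled draws**

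| Visit | Drug dispensed | ALT, AST, alk phos | Total bilirubin |
|---|---|---|---|
| Day 1 | yes | yes | yes |
| Week 11 | yes | yes | no |
| Week 23 | yes | yes | no |
| Week 28 | no (last at week 27) | no | yes |
| Week 32 | no | yes | yes |

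After day 1, transaminases and bilirubin are next scheduled together at week 32, when dosing is over.

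**Intervals** (later target day minus earlier)

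- Bilirubin as planned, to week 28: 197 − 1 = **196 days**, with no scheduled draw in between.
- ALT, AST and alkaline phosphatase: 78 − 1 = 77; 162 − 78 = 84; 225 − 162 = 63. The longest is **84 days**.
- Bilirubin if assayed with the liver function tests and kept at week 28: 77, 84 and 197 − 162 = 35. The longest is **84 days**.

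**Which rises are missed**

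- AST or ALT above 3 × ULN: Appendix A requires bilirubin within 24 hours, so the rise is covered.
- Drug already withheld for potential liver injury, for example alkaline phosphatase above 8 × ULN: covered by the same provision.
- Bilirubin above 3 × ULN with neither of these: no scheduled test until week 28. By then nothing more is dispensed, so a withhold would have little effect.

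The permanent-discontinuation rule in 6.3.1 needs a transaminase rise as well, so the reflex testing largely protects it. The gap is confined to the isolated-bilirubin criterion.

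**The case against.** The strongest reply is that Table 5 lists analytes and does not set timing. Phosphorus is in the same chemistry column yet is drawn at many treatment visits. That is so because phosphorus has its own entry in another row of Table 4; bilirubin has no such entry, so the comparison does not supply a test.

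The laboratory may in practice run bilirubin with the liver function tests. Section 6.3 names it among the hepatic laboratory values, and the SAP groups it there. The laboratory manuals are not available for this review and cannot confirm this; the protocol describes them as covering collection, handling and shipping. If they do bundle it, the correction only aligns the protocol with practice.

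Another reading is a deliberate two-step screen: enzymes first, bilirubin on a signal. That is a defensible design for combined injury. It does not fit a rule that acts on bilirubin alone.

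Several points do stand and limit the weight of the concern:

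- The 6.3.2 criteria are worded as recommendations.
- The documents give no frequency for isolated rises above 3 × ULN, and some would be benign.
- Exclusion 216 applies only after a gap of more than 14 days and says nothing about on-treatment frequency.
- The main stated hazard of excess exposure, hypocalcemia, is watched through weekly ionized calcium.
- Section 7.2 allows collected blood to be tested for safety, though this is discretionary.
- The week 28 sample may still reflect on-drug bilirubin, though too late to change dosing.

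**Conclusion.** The concern holds. Following the protocol as written, a subject who remains on study has no scheduled bilirubin between day 1 and week 28, and the stand-alone bilirubin criterion cannot be triggered by a scheduled test in time to affect dosing. The conclusion rests on reading Tables 4 and 5 together as the schedule, and it would be weaker in practice if the laboratory already assays bilirubin at weeks 11 and 23.

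This is a narrow safety-monitoring gap. It does not alter any endpoint estimate, and no number of affected subjects can be derived from the documents. It should still be corrected, because the remedy is cheap and the protocol has already decided that the value matters.

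**What to change.** In protocol Table 5, list total bilirubin under liver function tests, so that it is assayed at day 1 and weeks 11, 23 and 32. Keep it in the chemistry panel at week 28 as well. Amend the central-laboratory panel specification to match.

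The cost is one table correction plus one extra assay at each of two visits: at most 2 × 78 = 156 assays if all 78 subjects enrol and attend both. The samples are already drawn at those visits, so no visit or venipuncture is added. The downside is that some isolated rises will have a benign cause, such as Gilbert's syndrome (listed in 6.3.1), and may lead to a temporary withhold while the cause is checked.
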